6.4.3 Vital Signs

The analysis of vital signs includes blood pressure and pulse measurements. Averages of non-missing values will be calculated and used for the statistical analysis. If only 1 of the planned measurements is available, this value will be used.

Vital signs values will be summarized by treatment group and visit using descriptive statistics including absolute changes from baseline. The analysis will be repeated for SBP stratified by baseline SBP <130 mmHg, 130 to <160 mmHg and \geq 160 mmHg and SBP above and below median.

6.4.4 Weight and BMI

The values and the changes from baseline will be summarized by treatment group and visit using descriptive statistics for weight and BMI.

7. Document history and changes in the planned statistical analysis

SAP version 0.1 dated 14 DEC 2015 submitted for internal review

SAP version 0.2 dated 29 JAN 2016 submitted to the FDA

SAP version 0.3 dated 08 JUL 2016 submitted for internal review

Approved SAP version 1.0 dated 03 AUG 2016

Approved SAP version 2.0 dated 29 MAY 2019

Approved SAP version 3.0 dated 10 OCT 2019

Approved SAP version 4.0 dated 01 APR 2020

Approved SAP version 5.0 dated 05 NOV 2020

Approved SAP version 6.0 dated 15 FEB 2021

7.1 Overview of Changes to SAP – from version 1.0 to version 2.0

Editorial, administrative, and typographical corrections were made that do not affect the content of the overall integrated SAP. These changes are not described in this section.

The SAP, Version 1.0, dated 03 AUG 2016, was amended with the changes resulting from global CSP amendments, the latest being global amendment 4, forming integrated CSP

Version 3.0, dated 12 MAR 2019. SAP modifications resulting from the integrated CSP version 3.0 are primarily:

- administrative, typographical and consistency-related corrections,
- definition of treatment-emergent adverse events and laboratory parameters to also consider temporary interruptions of study drug as well as modification of special safety variables for hyperkalemia and worsening of renal function to only consider permanent discontinuations of study drug, and
- replacement of the date of first intake of study drug with the randomization date as the baseline date for all analyses (except those explicitly requiring start of study drug intake as a reference).

In addition, the following changes were introduced in SAP Version 2.0, dated 29 MAY 2019.

Modification 1: Update on sample size

Rationale: Due to the lower-than-expected event rate, the sample size of the study was increased by approximately 1000 subjects. As this has no impact on the original planning assumptions, the protocol text remained unchanged, but for descriptive purposes the expected sample size was added in the SAP

Sections affected:

- Section 3: Study Design

Modification 2: Exclusion from analysis sets due to critical GCP violations

Rationale: After detection of issues with investigator fraud and duplicate subjects, it was decided and agreed with the FDA to exclude the affected subject records from all analysis sets (except for the listings only set) as this data could not have been trusted.

Sections affected:

- Section 3: Study Design
- Section 5: Analysis Sets

Modification 3: Types of events used for efficacy analyses

Rationale: It was clarified that only events adjudicated by an independent adjudication committee will be used for all efficacy analyses (except for those explicitly mentioning investigator-reported events).

Sections affected:

- Section 4.1: General Principles
- Section 6.2.1.1: Primary efficacy variable: primary analysis

Modification 4: Stratification groups

Rationale: It was clarified that if the corrected stratification group (due to incorrect allocation at randomization) does not exist in the study, the stratification group the investigator originally specified in the IxRS will be kept. This is in line with the randomization and ensures that no strata with few patients are opened up which would result in potential non-convergence of the stratified Cox model, for example.

Sections affected:

- Section 4.1: General Principles

Modification 5: Handling of missing data for study drug exposure, clinical events, UACR at Month 4 and adverse events

Rationale: Texts were added to describe the handling of missing data for study drug exposure (conservative approach maximizing time on higher dose, but avoiding overlaps) and for clinical events (elaboration on median imputation rule). The handling of missing start dates for adverse events was simplified and aligned with the definition of treatment-emergence (see change related to Integrated CSP Version 3.0 above). For the analysis of UACR at Month 4, it was clarified that the closest set of measurements in the timeframe of Month 4, i.e. on days 120 (+/-30days), is used, regardless of whether it is labeled as the month 4 visit to also consider unscheduled visits or other visits in case these should be closer to the relevant date.

Sections affected:

- Section 4.3: Handling of Missing Data

Modification 6: Primary analysis when stopping at the interim analysis

Rationale: The significance level which would remain for the final analysis after conducting the interim analysis was made more precise and specified as 4.967388%. Furthermore, it was clarified that in case of stopping at the interim analysis, the primary analysis reported in the CSR will take all events up to the subjects' respective EoS visits into account as would be the case for the final analysis if the study does not stop prematurely.

Sections affected:

- Section 4.4: Interim Analysis and Data Monitoring

Modification 7: Derivation of the coefficient of variation, window for on-treatment/PPS analysis and baseline flag for UACR

Rationale: The formula for the coefficient of variation was added. The time window to consider unscheduled measurements in case a scheduled measurement is missing at a given visit for an efficacy analysis and to consider for the on-treatment analysis was set to 30 days in line with the time window for the on-treatment analysis/PPS analysis for clinical events.

The 30 days window also applies to investigator-reported clinical events. However, a 3 days window is still used for any safety analyses of UACR. In addition, the derivation of baseline UACR was clarified to require a set of two non-missing values on or before day of randomization; otherwise the screening set of UACR measurements would be used.

Sections affected:

- Section 4.5.3: Other data handling
- Section 6.2.3.6: Outcome events reported by the investigators

Modification 8: eGFR and UACR values after onset of ESRD for efficacy analyses

Rationale: It was clarified that UACR and eGFR values after onset of ESRD would be excluded from all efficacy analyses because they would be strongly related to the event of ESRD and thus would not be meaningful in themselves.

Sections affected:

- Section 4.5.3: Other data handling

Modification 9: Addition of subgroup factors and analyses for medical history and concomitant medications

Rationale: Additional subgroup factors (UACR at baseline below and above median and potency of concomitant CYP3A4 inducer medication) were added for reasons of completeness. A new analysis was added for concomitant medications ongoing at baseline, i.e., at randomization, which was not adequately captured before as the other analyses for concomitant medication are in relation to the dates of first intake of study drug, and which is also relevant considering that there are several subgroup factors for concomitant medications at baseline. Furthermore, analyses for concomitant medications and medical history will also be repeated on the SAF because it is certain that the SAF will differ from the FAS.

Sections affected:

- Section 4.5.4: Subgroup Analyses
- Section 6.1.3: Medical History
- Section 6.1.4: Prior and Concomitant Medications

Modification 10: Titration status

Rationale: The analyses for titration related to different questions on the eCRF were restructured and split up into three different analyses/tables for easier interpretability.

Sections affected:

- Section 6.1.5: Treatment duration, extent of exposure and compliance

Modification 11: Description of primary analyses for the primary and secondary efficacy time-to-event variables

Rationale: The description of the hypotheses was made more accurate by adequately taking into account the stratification factors. At the same time, survival rates were exchanged with hazard rates to create an obvious link from the hypothesis to the hazard ratio which is given as the primary output of the Cox model. However, this exchange has no impact on the content, as survival rates and hazard rates can be translated into each other and the hypotheses of equality of survival rates and of equality of the hazard rates (per stratum) are thus equivalent. Furthermore, the SAS code for the Cox model was corrected to the stratified Cox model specified in the text (by means of adding the stratification factors to the STRATA statement).

Sections affected:

- Section 6.2.1.1: Primary efficacy variable: primary analysis

Modification 12: Modifications and additions to the sensitivity analyses for the primary and secondary efficacy variables

Rationale: The analysis of number of (recurrent) events per 100 patient-years was replaced by an analysis of incidence rate, no longer considering recurrent events because this is not meaningful for the clinical events in this study as most of them usually do not happen more than once. An on-treatment analysis was added for the FAS in line with the protocol. Further supportive analyses were added to check the proportional hazards assumption for the Cox model (plot of the log of the negative of Kaplan-Meier estimates versus log time and Cox model including treatment by log-transformed time as an interaction). More details were given for the tipping point analysis, and it was clarified that this analysis and the newly added on-treatment analysis will only be done for the primary and key secondary renal endpoint based on the FAS.

Sections affected:

- Section 6.2.1.2: Primary efficacy variable: supportive analysis
- Section 6.2.2.2: Secondary efficacy variables: supportive analysis
- Section 9.1: Appendix A: Technical details missing data imputation model for time to event

Modification 13: Censoring rules for on-treatment/PPS analysis of key renal endpoint

Rationale: Censoring rules for the key secondary renal composite endpoint were clarified to consider both the time window of 30 days after treatment discontinuation as usual for this type of analysis in this SAP and the 5 months after the last visit with information of all components of the renal composite endpoint as done for the FAS analysis of this endpoint.

Sections affected:

- Section 6.2.2.2: Secondary efficacy variables: supportive analysis

Modification 14: Modification of list of further efficacy time-to-event endpoints

Rationale: Further exploratory time-to-event endpoints were added for the sake of completeness to adequately depict all the single components as well as reasonable sub-composites of the previously mentioned primary and secondary composite endpoints.

Sections affected:

- Section 6.2.3.1: Exploratory time to event variables

Modification 15: Deletion of analysis for relationship between a change in UACR from baseline to month 4 and the incidence of cardiovascular and renal events

Rationale: This analysis was removed because it was not deemed appropriate to compare the relationship between two post-baseline events in the described manner as the possibility of confounding with the factor treatment cannot be excluded.

Sections affected:

- Section 6.2.3.2: UACR and albuminuria

7.2 Overview of Changes to SAP – from version 2.0 to version 3.0

Major changes compared to version 2.0:

- Full specification of testing procedure and multiplicity adjustment, moved to new section 4.7.
- Deeper specification of imputation rules for missing event dates (section 4.3)
- Correction of data handling for UACR measurements (section 4.5.3)
- Definition of subgroup analyses for safety events (section 4.5.4)
- Alignment of cut-off values for baseline UACR/blood pressure categories
- Drop of name of investigator in disposition tables (section 6.1.1)
- Deletion of information from the combined treatment and follow-up epoch (section 6.1.1)
- Correction of ACEIs/ARBs baseline analysis (section 6.1.4)
- Amount of missing data will be summarized (section 6.2.1.2)
- Superseding frequency tables at certain time points by more powerful KM estimates (section 6.2.1.2)
- Specification of UACR analysis (section 6.2.2.1)
- Specification of analysis for components of primary and secondary endpoints (section 6.2.3.1)
- Specification of censoring rules for exploratory efficacy variables (section 6.2.3.5)

- Clarification about analysis of certain safety parameters (Hyperkalemia, worsening of renal function) (section 6.4.1)

7.3 Overview of Changes to SAP – from version 3.0 to version 4.0

Major changes compared to version 3.0:

- Clarification on imputation rules for partially missing death dates (section 4.3)
- Additional subgroups added, “key” and “important” subgroups re-ordered (section 4.5.4)
- Platelet aggregation inhibitors (excluding heparin) added to the list of concomitant medications (section 6.1.4)
- Clarification that time-to-event analysis on-treatment and for PPS will be censored at the end-of-study visit (sections 6.2.1.2 and 6.2.2.2)
- Deletion of one endpoint and addition of three endpoints to the list of other exploratory efficacy variables (section 6.2.3)
- Specification of Toeplitz as first choice alternative covariance matrix in case of convergency issues in PROC MIXED (sections 6.2.3.2, 6.2.3.3, 6.2.3.4)
- Deletion of analyses for the iohexol substudy, since the results of the substudies will be reported separately, and not in the clinical study report (section 6.2.3.3)
- Clarification of terminology for eGFR slopes as total, chronic and acute (section 6.2.3.3)
- Change from time-to-event analyses to logistic regression for other exploratory efficacy analyses (New diagnosis of atrial fibrillation, new diagnosis of heart failure and regression of albuminuria) (section 6.2.3.5)
- A separate listing will be generated for all AEs excluded from the AE analysis due to double reporting in Japan (section 6.4.1)
- For the other safety events, summary will be provided once for all events and once for all treatment-emergent events (section 6.4.1)
- Alignment of use of “treatment-emergent” (for safety) and “on-treatment” (for efficacy) analyses (e.g., section 6.4.2)
- Wald confidence limits for treatment differences in certain laboratory parameters will be calculated, due to the computational burden of exact unconditional confidence limits (section 6.4.2)

7.4 Overview of Changes to SAP – from version 4.0 to version 5.0

Major changes compared to version 4.0:

- Addition of section 4.8 “Considerations with regard to the COVID-19 pandemic” and section 6.2.4 “Supportive efficacy analyses related to the COVID-19 pandemic” as well as descriptive analyses throughout sections 6.1 (Population characteristics) and 6.4.1 (Adverse events) to evaluate the impact of COVID-19

- Addition of subgroup analyses for any treatment-emergent hyperkalemia and addition of new subgroup factors mainly for safety (section 4.5.4)
- Removal of redundant medical history items (section 6.1.3)
- Addition of new concomitant medication of interest “Trimethoprim and derivatives” and extension of list of concomitant medications of interest included in shift table for baseline vs. post-baseline use (section 6.1.4)
- Modification of overall titration status table to also include number of subjects up-titrated at least once and down-titrated at least once and addition of new table for number of subjects on 10 mg, 20 mg and on an interruption of study drug at specific time points (6.1.5)
- Clarification of Kaplan-Meier summaries and curves to present cumulative incidence probabilities and to include calculation of NNTs (section 6.2.1.2)
- Extension of the FAS on-treatment analysis to all secondary efficacy variables and to also include Kaplan Meier summaries and curves (sections 6.2.1.2 and 6.2.2.2)
- Modification of description for table on missing data for endpoint follow-up to also include ratio of observed to expected follow-up time (section 6.2.1.2)
- Addition of exploratory efficacy endpoints: Time to stroke, time to myocardial infarction, time to first occurrence of the composite endpoint of CV death, hospitalization for HF or non-fatal myocardial infarction, and time to first occurrence of the composite endpoint of CV death for HF or HF hospitalization (section 6.2.3)
- Clarification of wording for definition of shifts in albuminuria shift table (section 6.2.3.2)
- Modification of correlation analysis for acute vs. chronic eGFR slopes to be repeated by treatment group (section 6.2.3.3)
- Addition of new table for concomitant medications taken as treatment for treatment-emergent hyperkalemia (6.4.1)
- Clarification of technical details for missing data imputation for UACR at Month 4 in Appendix B (section 9.2)

9.1 Appendix A Technical details missing data imputation model for time to event

To investigate the impact of missing data under a missing not at random (MNAR) assumption a methodology similar to pattern-mixture-models will be employed as described by Little et al. (2016) [6]. In this approach, a Weibull survival model will be fitted to all subjects who prematurely discontinued study treatment in order to estimate the individual hazard rates for patients with withdrawn consent or loss to follow-up, but without a previous endpoint event. Based on these individual hazard estimates at the time of censoring (possibly penalized through inflation), event times for patients alive but censored before the global cut-off date (notification of study termination + 4 weeks) will be imputed.

Details:

The SAS LIFEREG procedure will be used where the natural logarithm of the survival time $w = \log(t)$ is modeled. The survival function has the form

$$S(w) = \exp\left(-\exp\left(\frac{w - \mu}{\sigma}\right)\right),$$

where μ is the location parameter (intercept) and σ is the scale parameter in the SAS output.

The observed hazard rates (scale and shape parameters) for individual subjects are obtained from a Weibull model fitted to all subjects who prematurely discontinued study treatment, adjusted for treatment group (coded 0=placebo, 1=finerenone) and the stratification factors. The Weibull probability density function is re-parametrized to have the following form

$$g(t | \lambda, \beta) = (\beta/\lambda) (t/\lambda)^{\beta-1} \exp(-(t/\lambda)^\beta),$$

where $\lambda = \exp(\mu)$ is the new scale parameter and $\beta = 1/\sigma$ is the re-parametrized shape parameter.

With this re-parametrization, the hazard function is given by

$$h(t | \lambda, \beta) = (\beta/\lambda) (t/\lambda)^{\beta-1}$$

and the survival function can be written as

$$S_2(t) = \exp(-(t/\lambda)^\beta).$$

For subjects with consent withdrawn or who are lost to follow-up and who did not experience a primary efficacy endpoint, random variables will be simulated using the conditional time to event distribution after the last contact date given that no event was observed before. If this randomly generated variable has a value less than the elapsed time between the last contact date and the global cut-off date, i.e. the date when all subjects should have performed their EOS visit (notification of study termination + 4 weeks), the subject will be counted as having observed an event at the last contact date plus the random variable. Otherwise, the subject is re-adjusted to be censored at the global cut-off date.

These imputed events will be added to the observed events in the study and the primary efficacy variable will be re-analyzed. This process will be repeated 1000 times. For the final analysis, the hazard ratio with 95.032612% confidence intervals (adjusting for the interim analysis) will be estimated for each imputed data set and then combined using standard multiple imputation combining rules.

Details:

When the survival time T follows a Weibull distribution with survival function S_2 , then the conditional distribution function of time T after the last contact date/censoring date (LC) is given for $x \geq 0$ by:

$$\begin{aligned} y &= \Pr(T \leq x + LC | T > LC) = 1 - \Pr(T > x + LC | T > LC) \\ &= 1 - \frac{\Pr(T > x + LC)}{\Pr(T > LC)} = 1 - \frac{S_2(x + LC)}{S_2(LC)} \end{aligned}$$

With the estimated shape parameter β and the scale parameter λ from the underlying Weibull model, this results in:

$$\begin{aligned} y &= 1 - \exp\left(-\left(\frac{x + LC}{\lambda}\right)^\beta\right) / \exp\left(-\left(\frac{LC}{\lambda}\right)^\beta\right) \\ &\equiv \log(1 - y) = -\left(\frac{x + LC}{\lambda}\right)^\beta + \left(\frac{LC}{\lambda}\right)^\beta \\ &\equiv x = \lambda \times \left(\left(\frac{LC}{\lambda}\right)^\beta - \log(1 - y)\right)^{1/\beta} - LC \end{aligned}$$

If y is replaced with a random variable with uniform distribution between 0 and 1, the random variable x can be generated using the inverse transformation technique from

$$\lambda \times \left(\left(\frac{LC}{\lambda}\right)^\beta - \log(1 - rand('uniform'))\right)^{1/\beta} - LC.$$

In addition, the estimated hazard rates for the finerenone group will be inflated by a known factor k , with 1000 simulations performed at each rate of inflation. Inflation will be done until

the upper limit of the confidence interval of the combined estimate of the hazard ratio crosses 1.

Details:

The imputation above is repeated with different inflation factors for the subjects in the finerenone group. The individual hazard rates is multiplied with k , leading to

$$k \times (\beta/\lambda) (t/\lambda)^{\beta-1}$$

with new scale parameter $s = \lambda/(k^{1/\beta})$.

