6.2 Efficacy

6.2.1 Analysis of primary efficacy variable

6.2.1.1 Primary efficacy variable: primary analysis

The primary efficacy variable is the time to first occurrence of the composite endpoint of CV death or non-fatal CV event (i.e. myocardial infarction, stroke, or hospitalization for HF). All events classifying for the primary endpoint have to be adjudicated positively by an independent adjudication committee.

The primary analysis of the primary efficacy variable will be performed in the FAS.

Events for inclusion in the primary analysis will be counted from the day of randomization (planned at Visit 1) onwards until the EOS visit following the study termination decision, or until the date of EOS notification + 4 weeks, if the EOS visit has not been performed. In the event of premature discontinuation from the study with no subsequent follow-up information, events will be counted up to the day of withdrawal from the study or non-CV death.

Randomized subjects without an event of the primary composite endpoint at the time of analysis will be censored at the date of their last contact up to and including the EOS visit or date of non-CV death. Subjects without any information about the primary composite endpoint after baseline will be censored at Day 1.

The hierarchical testing procedure which will be used for the primary and secondary efficacy variables is described in section [4.7](#).

In order to evaluate whether finerenone is superior to placebo in prolonging the time to the first event of the primary composite endpoint, the following null hypothesis will be tested using the logrank test at the two-sided significance level given above:

$$H_0: \lambda_{finerenone,k}(t) = \lambda_{placebo,k}(t) \text{ for all time points } t \geq 0 \text{ and each stratum } k$$

The alternative hypothesis will be:

$$H_1: \lambda_{finerenone,k}(t) \neq \lambda_{placebo,k}(t) \text{ for at least one time point } t \geq 0 \text{ and at least one stratum } k,$$

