- Estimate the hazard at time of loss to follow-up, using a Weibull survival model fitted to the population of subjects who prematurely discontinued study treatment and adjusted for treatment group and stratification factors.
- Inflate the hazard only in the finerenone group by a known factor; assumes non-informative censoring in the control group.
- Impute events to the end of the study 1000 times, calculate the hazard ratios with the stratified Cox model specified in section 6.2.1.1 and combine them using standard multiple imputation combining rules.
- Increase the inflation factor until upper limit of two-sided 95.032612% (or 99.73% at the interim analysis) confidence interval for the hazard ratio crosses 1.0; this will be the “tipping point”.

The tipping point will show how much higher the event risk after drop-out would need to be in the finerenone group so that statistical significance is lost. Since there is no particular reason to assume that the event rate should be higher, a large tipping point will indicate robustness of the study results. Technical details of the model are provided in section 9.1.

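### The Weibull behind the tipping-point analysis mixes on-drug and off-drug risk, so the inflation factor cannot be read as excess risk after drop-out; the direction of the distortion is unknown

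*SAP*

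**What the plan says.** SAP 6.2.1.2 plans a tipping-point analysis for subjects who are lost to follow-up or withdraw consent. The hazard is estimated "using a Weibull survival model fitted to the population of subjects who prematurely discontinued study treatment", adjusted for arm and strata, and Appendix A (9.1) repeats this: "a Weibull survival model will be fitted to all subjects who prematurely discontinued study treatment in order to estimate the individual hazard rates". In the appendix, "random variables will be simulated using the conditional time to event distribution after the last contact date given that no event was observed before". The distribution comes from the ratio S2(x + LC)/S2(LC), where LC is the time of last contact. The estimated shape and scale are inserted as fixed values, and only a uniform random number varies across the 1000 data sets. The resulting hazard ratios are "combined using standard multiple imputation combining rules".

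The penalty k is defined thus: "Inflate the hazard only in the finerenone group by a known factor; assumes non-informative censoring in the control group". It is increased until the 95.032612% interval reaches 1. The stated reading is that "The tipping point will show how much higher the event risk after drop-out would need to be in the finerenone group" for significance to be lost, and a large value is taken as a sign of robustness. No threshold is given. SAP 6.2.2.2 repeats the analysis for the key secondary endpoint.

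Appendix A does not state the time origin. SAP 6.2.1.1 says "Events for inclusion in the primary analysis will be counted from the day of randomization", and the ratio above puts the fitted time and LC on one clock. Randomization is the only origin consistent with both.

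**The concern.** Membership of the fitting set is decided by a later event, the drug stop, while the clock starts earlier. A subject who stops in year 2 brings the whole of year 1 on drug into the denominator. Subjects are expected to stay on drug after a non-fatal endpoint event (Protocol section 5, SAP section 3), so someone who has the event on drug and stops afterwards brings an on-drug event into the numerator. Nothing sets entry at the stop or requires the subject to be event-free then.

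The fitted hazard is thus a selected mixture of on-drug and off-drug risk, yet k is read as a multiple of risk after drop-out. The tipping point is the only inferential analysis of informative censoring that the SAP specifies for the primary endpoint, and it would be consulted mainly when the result is close to the boundary.

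**Working it through.** **Planning figures reproduced.** The inputs come from Protocol 10.4: placebo event rate 8% a year, hazard ratio 0.80, finerenone discontinuation 5% a year, loss 0.7% a year, accrual 33 or 41 months with 11 or 7 further months. A Markov log-rank calculation gives 972 events and N = 6230, and 979 events and N = 6305. The plan states 970 and 6212, and 976 and 6286, so agreement is within 0.3%. The final significance level recomputes to 0.049674 against 0.04967388 in SAP 4.7, and 1 − 0.04967388 = 0.95032612 matches the interval level used for the tipping point. The documents give no figure for the Weibull itself.

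**Assumptions not in the documents.** 30% of first events fatal; off-drug hazard 1 to 2 times placebo; 0 to 30% of non-fatal events trigger a stop; on-drug death is not a stop; equal stop rates in both arms.

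**Why the fit can err either way.** Let p be the share of fitted person-time before the stop and q the share of fitted events at or before it. With constant hazards:

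- fitted hazard = events / time
- post-stop hazard = (1 − q) × events / [(1 − p) × time]
- ratio of fitted to post-stop = (1 − p)/(1 − q)

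Simulation at the planning rates gave p = 0.50 to 0.60 and q = 0.26 to 0.77. The widest pairings are (1 − 0.60)/(1 − 0.26) = 0.40/0.74 = 0.54 and (1 − 0.50)/(1 − 0.77) = 0.50/0.23 = 2.17. The ratio is 1 only if p = q.

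**Simulated ratio of the SAP-fitted hazard at last contact to the true off-drug hazard** (N = 7400 as in SAP section 3, 41 + 7 months, 12 replicates per scenario):

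| Off-drug risk vs placebo | Non-fatal events triggering a stop | Placebo | Finerenone |
|---|---|---|---|
| 2 times | none | 0.63 | 0.56 |
| 1 times | none | 0.87 | 0.77 |
| 2 times | 30% | 1.14 | 1.03 |
| 1 times | 30% | 1.96 | 1.62 |

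A Weibull with delayed entry at the drug stop gave 0.87 to 1.08. Repeat simulations at the planning rates gave 0.66 to 1.99 for the hazard, and 0.68 to 1.97 for the cumulative hazard. Restarting the clock at the stop brought the latter to 0.96 to 1.04.

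**Effect on k.** Six significant trials per cell, a coarse grid for k, and the placebo hazard multiplied by 0.85.

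- Observed hazard ratio about 0.865, off-drug risk 2 times, no triggered stops: k was 2.5 to 6 under both fits. The SAP fit was higher in 4 trials and equal in 2.
- Same hazard ratio, off-drug risk 1 times, 30% triggered: k was 2 to 4 under the SAP fit and 2 to 5 under the post-stop fit. The SAP fit was lower in 4 trials and equal in 2.
- Observed hazard ratio about 0.80, both scenarios together: the result had not tipped by k = 10,000 in 8 of 12 trials under the SAP fit and 7 of 12 under the post-stop fit.

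Few subjects drive this. Mean follow-up is (7 + 41/2)/12 = 2.29 years, so expected finerenone losses are about 3700 × 0.007 × 2.29 = 59 before removing earlier events. The simulated trials had 38 to 73.

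**Fixed parameters.** The largest change in the pooled standard error of the log hazard ratio was 0.0635 to 0.0638, or 0.0003/0.0635 = 0.5%. The fraction of missing information was 1.1 to 2.4% with fixed and 1.3 to 2.6% with drawn parameters.

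**The case against.** The SAP names its target as the hazard when follow-up is lost and uses drug-stoppers as a proxy group for lost subjects; off-drug risk is not its term. The method follows a cited paper on missing data in a large cardiovascular outcomes trial, which was not available for this check. The SAP sets no cut-off for k, so a moderate shift may not alter the reading. Appendix A also yields an uninflated pooled hazard ratio with its interval. SAP 6.2.1.2 adds a summary of missing follow-up by arm, and Protocol 10.3.3.2 and 11.4 promise other imputation rules. The primary test does not depend on any of this. These points limit the importance of the concern. They do not remove it, because SAP 6.2.1.2 itself reads k as excess risk after drop-out.

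Two stronger readings are tempting.

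- A reader might infer that k is overstated and falsely reassuring. A comparison with 14 simulated trials per scenario gave k of 16.3 against 12.5 (ratio 1.30) and 8.4 against 7.1 (ratio 1.18). It assumed stops unrelated to events, and it changed the clock and added parameter draws together. When events trigger stops, the difference can reverse. The documents do not say which applies.
- A reader might infer that fixed parameters make the interval materially too narrow. At the planned loss rate they do not; the effect would grow with much higher loss.

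**Conclusion.** The concern holds in a limited form. The reference hazard for k mixes risk before and after the drug stop, and under the assumptions listed it lies at about 0.6 to 2.0 times the true post-stop hazard. Dilution by on-drug time pulls it down; events that lead to a stop push it up; some scenarios land near 1. Neither the direction nor the size for this trial follows from the documents, so k is not interpretable on the scale the SAP gives it.

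The conclusion rests on reading the clock as time from randomization, which is implied but not written, and on assumed event-related stopping and off-drug risk. The simulations address the primary endpoint only. This is a sensitivity analysis, and the choice of fit matters mainly for a result near the boundary, so it is a worthwhile refinement rather than a threat to the trial's conclusion.

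**What to change.** In SAP 9.1 and 6.2.1.2:

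- State the time origin. Start the Weibull clock at permanent drug stop, include only subjects event-free at that date, and impute from time since stop. For subjects lost with no earlier recorded stop, set the stop at last contact.
- State whether a death on drug counts as premature discontinuation.
- Report the implied absolute event rate after drop-out, by arm, beside each k.
- As a secondary correctness point, draw the Weibull parameters from their estimated covariance at each imputation, or refit on a bootstrap sample, so that the combining rules apply. The UACR imputation in SAP 9.2, run with PROC MI and MCMC, already draws its parameters.

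The cost is revised wording and modest reprogramming; PROC LIFEREG can fit the restarted clock. Fewer events will inform the fit, so the reference hazard will be less precise. No new data are needed and the primary analysis does not change.
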